| Local Tolerability (7)                |   | X |       | X | X |        | X      |
| Dispense subject diary                |   | X |       | X |   |        |        |
| Collect and review subject diary      |   |   |       | X | X |        | X      |
| Safety phone call (9)                 |   |   | x (9) |   |   | x (10) |        |

- (1) Early termination visit should – if possible - be conducted 28±3 days after last IMP administration.
- (2) Systolic/diastolic blood pressure, pulse rate, body temperature
- (3) Conditions/symptoms noted prior to randomization should not be reported as AE, but should be reported as medical history
- (4) Medications administered up to 30 days prior to screening until end of study participation should be documented
- (5) The clinical laboratory comprises: Hematology (hemoglobin, hematocrit, erythrocyte count, differential white blood count, platelets), Chemistry (creatinine, potassium, sodium, calcium, AST, ALT, alkaline phosphatase, bilirubin), Coagulation (prothrombin time (PT), activated partial thromboplastin time (aPTT), fibrinogen), Urinalysis (standard urine test stick for determining pH-value, glucose, protein, bilirubin, urobilinogen, red blood cells, white blood cells, nitrite, ketone and specific gravity), Virology (only at screening; HBs-Ag, anti-HBc-Ab, anti-HCV-Ab, HIV 1/2 Ab/HIV-1 Antigens if not done within 30 days before screening)
- (6) To be performed if necessary, according to findings in symptom-directed physical examination
- (7) To be performed 1 hour after each IMP administration and additionally at the subsequent visit (prior to IMP administration, if applicable)
- (8) Participants should be interviewed regarding potential AEs since the last study visit. If indicated, participants should be called in for an unscheduled visit.
- (9) The post dose safety call follows up should be conducted 7±1 days (one week) after the first vaccination.
- (10) The post treatment safety call follows up should be conducted 182 days (6 months) after the first study treatment also in case of an early termination.
- (11) The amount of blood sample taken during the early termination (ET) visit depends on the time point of the visit. If the ET-visit replaces the primary endpoint visit on day 56±3, 48 to 60 mL blood should be taken; otherwise 24 to 48 mL are enough.
- (12) Urine for pregnancy test should be taken before vaccination

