### **8.7 Early Termination Visit (ET)**

Participants who are withdrawn or wish to discontinue the study prematurely for any reason shall be asked to attend an early termination visit.

If the early termination occurs within the treatment period (at or before Visit 4), participants shall perform all procedures as defined for Visit 3. If the early termination occurs within the follow up period (after Visit 3), participants shall perform all procedures defined for Visit 4.

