## **8.8 Unscheduled Visits**

Unscheduled visits can be conducted whenever deemed necessary. The extent of the examination performed at an unscheduled visit is at the discretion of the investigator. All procedures completed during an unscheduled visit should be documented in the source data and should also be entered to the electronic case report form (eCRF).

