### **8.11.1 Samples for Safety Laboratory Parameters**

Safety laboratory parameters will be analysed by local laboratories according to applicable laboratory SOP.

The following parameters will be measured to evaluate inclusion and exclusion criteria only once at screening visit (SV).

- Virology: Hepatitis B surface-Ag, anti-Hepatitis B core-Ab, anti-Hepatitis C-Ab, HIV Ab. HIV tests that were performed up to 30 days before screening and where results are available are acceptable and do not require a new test.

The following laboratory parameters will be assessed for subject's safety at screening (VS), Visit 2, Visit 3 and additionally at Early Termination (if applicable) as depicted in Table 2.

- Haematology: haemoglobin, haematocrit, erythrocyte count, differential and total white blood count, platelets
- Chemistry: creatinine, potassium, sodium, calcium, AST, ALT, alkaline phosphatase, bilirubin
- Coagulation parameter: prothrombin time (PT), activated partial thromboplastin time (aPTT), fibrinogen
- Urinalysis: a standard urine test dipstick for determining pH-value, glucose, protein, bilirubin, urobilinogen, blood, leucocytes esterase, nitrite, ketone and specific gravity will be used.
- Laboratory values deviating from the normal ranges defined by the local laboratory will be evaluated by the investigator. Clinically relevant deviations have to be reported as adverse events and graded according to the FDA Guidance for Industry (Toxicity Grading Scale for Healthy Adult and Adolescent Volunteers Enrolled in Preventive Vaccine Clinical Trials, Sept. 2007)

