## 2.8 Handling Missing Data

Generally, missing values will not be imputed, and the analysis will be limited to observed values. But for missing data in the AE (e.g. missing information about seriousness, severity or causality) a worst case approach will be applied. For example, adverse events with missing severity assessments will be considered as “Potentially life threatening” and events with missing relationship to study treatment are counted as “Definitely” related to study treatment. In case of missing assignment to solicited or unsolicited, this AE will neither be counted in tables for solicited AEs nor in tables for unsolicited AEs but in tables for all AEs.

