## 5. IMMUNOGENICITY ANALYSIS

The immunogenicity analysis will be performed for the mITT and PP population. All tables will be presented by treatment group and overall. Data from the early termination visit or unscheduled visits will be listed only and will not be shown in summary tables by time point.

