### 6.2.2 *Derivations and Definitions*

- All solicited and unsolicited Adverse Events up to Day 56 (Visit 3) will be analyzed for the preliminary analysis and all AE in the database for the Final Analysis. The following rules will be applied to identify AEs up to Day 56 for preliminary analysis: In general, all AE with start date prior to or at Visit 3 are considered. If a subject has no Day 56 visit (Visit 3) then all AEs within 56 days from Visit 1 (Day 0) (Visit 1 + 56 days) are included. If start date of AE is incomplete (e.g. missing start day) and the AE could theoretically be within Visit 3, or if Visit 3 is not available, within 56 days from Visit 1 (Visit 1 + 56 days), it will be handled as AE up to Day 56 (Visit 3) and thus be included in the preliminary analysis. If start date of AE is unknown it will be handled as AE up to Day 56 visit (Visit 3) and thus be included in the preliminary analysis.
- Percentages for AE rates are based on N (treatment group totals).
- An Adverse Events is considered to be related to study treatment if “Relationship to Study Treatment” is answered with “definitely”, “probably” or “possibly” or the causality is missing.
- Tables showing “severe” events will include events with grade 3 or 4 or missing grade.
- In tables showing subjects with AEs by maximum severity, subjects will be counted only in the highest grading category (=“potentially life threatening”), but events will be counted in each reported grading category.

Adapted from:

STAT03\_A Statistical Analysis Plan

Version 6.0, Effective Date 16-Feb-2018

Confidential and intellectual property of Assign DMB. No part of this document or its contents may be duplicated, referenced, published or otherwise disclosed in any form or by any means without prior written consent of Assign DMB.

- In tables showing AEs by causality, subjects will be counted only in the strongest relationship category ("definitely"), but events will be counted in each category.

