## 6.3 Laboratory Parameters

Data from the early termination visit or unscheduled visits will be listed only and will not be shown in summary tables by time point. Laboratory data from scheduled visits (VS, Visit 2 and Visit 3) will be tabulated by time point. Specifications on TLFs are provided in Section 7:

For details on table and listing content, see Section 7.

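### SAP 5, 6.3 and 6.4 drop an in-window early-termination sample from the Day 56 tables and leave some abnormal laboratory values in listings only

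*Combined protocol and SAP*

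**What the plan says.** SAP 5 (Immunogenicity Analysis) states: "Data from the early termination visit or unscheduled visits will be listed only and will not be shown in summary tables by time point". The same sentence stands in SAP 6.3 for laboratory parameters and in SAP 6.4.1 for vital signs. SAP 6.3 adds: "Laboratory data from scheduled visits (VS, Visit 2 and Visit 3) will be tabulated by time point".

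In SAP 7.1, the immunogenicity tables (2.3.1.1 to 2.3.1.17, repeated for the per-protocol set), the laboratory tables (1.4.1.29 to 1.4.1.39) and the follow-up vital-sign tables (1.4.1.40 to 1.4.1.43) are all by visit or time point. No other post-baseline summary is planned in these domains.

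Protocol Table 2, footnote 1, places the ET visit 28±3 days after the last injection where possible. For an ET in the treatment period, Protocol 8.7 says "participants shall perform all procedures as defined for Visit 3". Footnote 11, on blood volume for the T-cell sample, provides for the case "If the ET-visit replaces the primary endpoint visit" on day 56±3. Protocol 8.8 says "Unscheduled visits can be conducted whenever deemed necessary" and leaves their content to the investigator.

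Adverse events follow a different route. Protocol 8.11.1 requires of laboratory results: "Clinically relevant deviations have to be reported as adverse events and graded according to the FDA Guidance for Industry". AEs enter the Day 56 tables by date: "In general, all AE with start date prior to or at Visit 3 are considered" (SAP 6.2.2). For an AE with no solicited/unsolicited type, SAP 2.8 says "this AE will neither be counted in tables for solicited AEs nor in tables for unsolicited AEs but in tables for all AEs".

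**The concern.** The protocol arranges for a participant who leaves after the second injection to give the Visit 3 samples at about the Visit 3 time. The SAP has no rule that uses them. It does not impute missing values (SAP 2.8), and withdrawn participants are not replaced (Protocol 8.9.2). The arms have 8 to 14 people, so each unused sample is a visible part of the Day 56 comparison.

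Safety laboratory parameters are a secondary endpoint in their own right (Protocol 6.2.2). After vaccination they are scheduled only at Days 28 and 56 (Table 2 and Protocol 8.11.1). The Day 7 call may bring a participant in for an unscheduled visit (Protocol 8.5.2), and any blood drawn then falls under the exclusion. At stake are some precision in the Day 56 immunogenicity tables and the completeness of the laboratory summaries.

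**Working it through.** There is no planned power or precision figure to reproduce. Protocol 12.4 says that no formal sample size calculation was done, and no SD, effect size or dropout rate is given. The allocation adds up: 14 + 14 + 12 + 8 = 48.

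**Step 1. Does an ET visit fall in the Visit 3 window?** The second injection is on day 28±3, that is, day 25 to 31. ET is 28±3 days later, and the Visit 3 window is 56±3, that is, day 53 to 59.
- Full range of ET days after the second injection: 25 + 25 = 50 to 31 + 31 = 62.
- Second injection on day 28: ET on day 53 to 59, exactly the Visit 3 window.
- Second injection on day 25: ET on day 50 to 56, with 4 of 7 days inside. On day 31: ET on day 56 to 62, again with 4 of 7 inside.
- Over all 7 × 7 = 49 permitted combinations, 37 fall inside. This counts day pairs and is not a probability.
- After the first injection only: ET on day 25 to 31, which is the Visit 2 window and not a stand-in for Day 56.

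**Step 2. Weight of one participant.** 1/14 = 7.1% (A or B), 1/12 = 8.3% (C), 1/8 = 12.5% (D).

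**Step 3. Precision, by assumption.** Suppose that 0, 1 or 2 participants per arm have only an in-window ET sample at Day 56. The standard error of the A versus D difference in log10 GMT is proportional to √(1/nA + 1/nD). The unadjusted 95% CI for the GMT ratio is the estimate divided and multiplied by 10^[t(0.975, N−4) × SD × √(1/nA + 1/nD)], with N = 48, 44 or 40. The log10 SD is assumed to be 0.3, 0.5 or 0.7. The exact upper 95% limit for no seroconverters among n in group D is 1 − 0.025^(1/n).

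| Lost per arm | nA, nD | √(1/nA + 1/nD) | SE change | CI factor, SD 0.3 / 0.5 / 0.7 | Upper limit, 0 of nD |
|---|---|---|---|---|---|
| 0 | 14, 8 | 0.443 | none | 1.85 / 2.80 / 4.22 | 36.9% |
| 1 | 13, 7 | 0.469 | +5.8% | 1.92 / 2.98 / 4.61 | 41.0% |
| 2 | 12, 6 | 0.500 | +12.8% | 2.01 / 3.21 / 5.13 | 45.9% |

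**Step 4. Following an abnormal laboratory value from an ET or unscheduled visit.**
- Judged clinically relevant: it is reported and graded as an AE (Protocol 8.11.1) and enters the AE tables by start date (SAP 6.2.2). It counts towards the primary endpoint if it starts by Visit 3, or within 56 days of Visit 1 where there is no Visit 3.
- Out of range but judged not clinically relevant: there is no AE, the by-visit tables exclude it, and it appears only in Listings 1.4.33 to 1.4.36. SAP 7.1 has no worst-value or any-visit table.

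**Step 5. Following an AE with no type flag.** It counts in the all-AE overview (Table x.4.1.2, which includes any SAE) and the maximum-severity table (x.4.1.7), and it is listed (x.4.3 and x.4.4). It is absent from the symptom tables (x.4.1.8 to x.4.1.12), which cover solicited events, and from the preferred-term, SOC/PT and causality tables (x.4.1.13 to x.4.1.28), which cover unsolicited events.

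**The case against.** Keeping unscheduled values out of by-visit means is ordinary practice, because such testing is selective and its extent is discretionary. A participant called in between visits still contributes Visit 2 and Visit 3 values. Laboratory data are descriptive here, and out-of-range values are listed by subject, visit and clinical significance, which is workable for 48 people.

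The ET problem is also narrow. It needs someone who leaves after the second injection yet attends within day 53 to 59. An ET after one injection comes at Visit 2 timing, and that participant has a major deviation for a missed vaccination (SAP 2.9), which may exclude them from the primary per-protocol set. The individual stopping rules end vaccination but not scheduled follow-up (Protocol 8.9.1). The wording on replacing the visit stands only in a footnote on T-cell blood volume; for VNT and ELISA it has to be inferred from the Visit 3 procedures and the ET timing. Immunogenicity is secondary.

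All of this stands, and it limits the size of the point. It does not supply the two missing pieces: a rule for an ET sample that meets the Visit 3 window, and a summary of laboratory abnormalities that counts every post-baseline visit. Nothing in SAP 2.9 or 2.11.3 excludes a participant from the per-protocol set merely for leaving after both injections, so the mapping can matter there as well as in mITT.

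**Conclusion.** The rule leaves usable in-window ET samples out of the Day 56 tables. It also leaves ET and unscheduled laboratory abnormalities below the AE threshold without a summary. The consequence is modest. The primary AE rate is unaffected. The immunogenicity effect depends on an unstated number of early terminations: under the assumption of one or two per arm, the A versus D standard error is 5.8% to 12.8% larger, and with none in the window nothing changes. The change is worth making because it is cheap.

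A reader might infer more than the documents support:
- *That these results miss every summary table, or that laboratory tests prompted by a problem never reach the safety tables.* The exclusion covers by-time-point tables in three domains. AE tables are not tied to scheduled visits, and clinically relevant deviations must be reported as AEs.
- *That the samples are lost.* They remain in the subject listings.
- *That the safety summaries are biased towards looking clean.* This would need evidence that the scheduled values are healthier than the excluded ones, and the documents offer none.
- *That the missing-flag rule contradicts the worst-case rule or could hide an SAE.* The worst-case rule gives seriousness, severity and causality as its examples. Event type has no obvious worst case and gets its own explicit rule in the same section. An unflagged SAE is still counted as an SAE in the overview.

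**What to change.** 1. In SAP 5, 6.3 and 6.4, assign an ET or unscheduled sample or measurement that falls in the Visit 2 or Visit 3 window (±3 days) to that visit when the scheduled one is missing. Apply this to the mITT immunogenicity tables and to the per-protocol tables where the participant otherwise qualifies; the laboratory and vital-sign tables stay on the safety population. State which sample is used if two qualify, for example the one nearest the target day.
2. Add a row for the worst value at any post-baseline visit to Tables 1.4.1.35 to 1.4.1.37, counting ET and unscheduled results, with values above and below range shown separately. Keep unscheduled values that are not mapped under item 1 out of the by-visit means.
3. As a minor point, add an all-AE SOC/PT table so that AEs without a type flag are shown by term. This avoids defaulting them to unsolicited, which could misclassify diary reactions.

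Protocol 8.7 describes a treatment-period ET as at or before Visit 4 and a follow-up ET as after Visit 3. These overlap and should be reconciled when the mapping rule is written.

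The cost is SAP wording and a little programming; out-of-range counts may rise slightly. The immunogenicity analysis is deferred to the final analysis (SAP 2.1), so item 1 fits there directly. The laboratory and vital-sign tables are numbered for the preliminary analysis only, and SAP 2.1 refers to that analysis in the past tense, so revised versions would have to be issued with the final analysis.

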### 5.1 Data points

The following information will be analyzed by visit descriptively in tables and corresponding details on the subject level will be provided in data listings:

- GMT of Zika-RSP VNT antibody (incl. ANOVA with fixed treatment group as described in Section 2.6)
- Seroconversion rate for Zika-RSP VNT antibody (incl. test as described in Section 2.6)
- Positive/Negative results for NT
- GMT of Zika-RSP-ELISA antibodies (incl. ANOVA with fixed treatment group)
- Seroconversion rate for Zika-RSP-ELISA antibodies
- Positive/Negative results for ZIKA ELISA
- GMT of Measles-ELISA antibodies (incl. ANOVA with fixed treatment group)
- Seroconversion rate for Measles-ELISA antibodies
- Positive/Negative results for MV ELISA
- specific functional CD4+ T-cells by visit (without geometric mean):
  - E+prM positive/negative
  - E values
  - prM values

Sampling details for VNT, ELISA Zika-RSP, ELISA measles and T-cells immunity (will be listed only)

Specifications on TLFs are provided in [Section 7](#).

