#### Potential Benefit

If the clinical development of MV-ZIKA-RSP is successful, this vaccine might help people, who are at risk of acquiring an infection with Zika virus and might help to prevent congenital effects occurring in infants of infected mothers.

A boost in measles immunity may be an additional benefit. The impact of pre-existing immunity is a major point of interest for Measles-vectored vaccines, as large parts of the population have been vaccinated at least once, while some have undergone natural infections. In previous phase I (Ramsauer et al. 2015) and phase II (Reisinger et al. 2018) clinical trials we have shown that the immunogenicity of another vaccine using the same vector (MV-CHIK) is not influenced by the levels of Measles-specific serum IgG before vaccination. In addition, we found that the frequency of Adverse Events (AEs) in participants with low (<200 iU/l) and participants with high ( $\geq 200$  U/l) frequency of anti-Measles IgG is similar ( $p=0.0658$  when comparing unsolicited AEs,  $p=1.0000$  when comparing solicited AEs).

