#### Enzyme linked immunosorbent assay (ELISA)

In addition, humoral systemic immune response mediated by serum IgG antibodies against zika-rsp will be determined by IgG ELISA.

At Visits 1, 2, 3 and ET (if applicable) a volume of 8 ml blood will be collected, to isolate serum and freeze a minimum of three aliquots (1 ml /round bottom cryovial) at -80°C for determination of anti-zika antibodies by ELISA.

Anti-measles antibodies will be determined by ELISA out of the same samples collected at Visits 1, 2, 3 and ET (if applicable). Therefor no additional blood sapling will be required for this assay.

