### 12.2 Methods of Statistical Immunogenicity Analysis

The immunogenicity analysis will compare the anti-zika-rsp VNT antibody geometric mean titre (GMT) in the Per Protocol (PP) analysis population between the treatment groups. GMTs and GMT ratios will be estimated by applying an analysis of variance including the factor treatment group. This will be done using  $\log_{10}$  transformed data and taking the anti-log of the resulting point estimates for the least squares means, least squares means differences and the corresponding 2-sided 95% CIs.

P-values will also be provided to compare GMTs between the treatment groups adjusted for multiple comparisons according to Tukey-Kramer. Seroconversion rates will be compared between groups using Fisher's exact test.

Seroconversion will be defined as anti-zika-rsp VNT titres  $\geq 20$ .

ZIKA-RSP- and measles- ELISA titres will be analysed as described above.

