## 2.6 Inferential Analyses

The analysis for primary endpoint will compare adverse events rates up to day 56 between treatment groups using Fisher-Freeman-Halton test. The same overall test between treatment groups will be performed for all adverse event tables in the Day 56 analysis as well as the final analysis.

The immunogenicity analysis will compare the anti-zika-rsp VNT antibody geometric mean titer (GMT) in the Per Protocol (PP) analysis population between the treatment groups. GMTs and GMT ratios will be estimated by applying an analysis of variance including the factor treatment group. This will be done using log10 transformed data and taking the anti-log of the resulting point estimates for the least squares means, least squares means differences and the corresponding 2-sided 95% CIs.

P-values will also be provided to compare GMTs between the treatment groups adjusted for multiple comparisons according to Tukey-Kramer.

For the primary immunogenicity analysis, values below the lower limit of detection are replaced by half of the limit and values above the upper limit are replaced by the upper limit.

As sensitivity analysis, an analysis of immunogenicity will be applied, that does not use such imputation. Therefore, observations will be interval-censored and GMTs will be estimated by assuming normal distribution for the log-transformed values (intervals). Values below the lower limit of detection will be left-censored at the lower limit and values above the upper limit (if applicable) will be right-censored at the upper limit.

Seroconversion rates and positivity rates will be compared between groups using Fisher-Freeman-Halton test.

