### 5.2 Derivations and Definitions

- For final analysis all time points, including Visit 1 (Day 0), Visit 2 (Day 28) and Visit 3 (Day 56) will be analyzed.
- Seroconversion rate for anti-zika-rsp VNT titers is defined as proportion of subjects achieving anti-zika-rsp VNT titers  $\geq 20$  at a certain time point.

- Seroconversion rate for anti-zika-rsp ELISA titers is defined as 4-fold increase over baseline (Visit 1 –Day 0). If no Visit 1 (Day 0) sample is available, no seroconversion will be determined.
- For MV ELISA, Zika ELISA, NT and T-Cell an analysis of positive versus negative values is planned. Since such a definition could not be discussed and communicated with the central laboratory at the time of generation of this SAP, details about used limits will be shown as footnotes in the corresponding tables and explained in the Clinical Study Report.
- For the different immunogenicity parameter there are different lower limit of quantification (LLOQ). [redacted]
  - In data listings, the original reported value “<LLOQ” will be displayed.
  - For calculations (GMT, median...) the half of the true LLOQ value will be used for such values.
  - If another unexpected value is reported as LLOQ in the data than mentioned here, the half value of the reported LLOQ will be used for the calculations.
- For the different immunogenicity parameters there are different upper limits of quantification (ULOQ) [redacted]
  - In data listings, the original reported value “>ULOQ” will be displayed.
  - For calculations (GMT, median...) the ULOQ value will be used for such values.
  - If another unexpected value is reported as ULOQ in the data than mentioned here, this ULOQ value will be used for calculations.
- For analysis using interval-censored data an interval will be defined for every observation. Observations between LLOQ and ULOQ will be handled as interval with left limit and right limit being the observed value. For values <LLOQ the interval will be left-censored with the LLOQ as right limit. For values >ULOQ the interval will be right-censored with the ULOQ as left limit.

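### The Day 28 and Day 56 GMT comparisons leave out the planned Day 0 titre: the ANOVA is valid but gives up precision, most clearly for measles ELISA and probably very little for Zika VNT

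*Combined protocol and SAP*

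**What the plan says.** The model is set out in protocol 12.2 and repeated in SAP 2.6: "GMTs and GMT ratios will be estimated by applying an analysis of variance including the factor treatment group". It is written there for Zika VNT on the log10 scale, with "corresponding 2-sided 95% CIs" and Tukey-Kramer p-values. Protocol 12.2 extends it to the other assays: "ZIKA-RSP- and measles- ELISA titres will be analysed as described above". SAP 5.1 lists it again as "GMT of Zika-RSP-ELISA antibodies (incl. ANOVA with fixed treatment group" and "GMT of Measles-ELISA antibodies (incl. ANOVA with fixed treatment group".

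Day 0 samples are planned for all three assays (protocol Table 2 and 8.11.2). For measles: "Anti-measles antibodies will be determined by ELISA out of the same samples collected at Visits 1, 2, 3 and ET (if applicable". SAP 5.2 treats Day 0 as a time point of its own: "For final analysis all time points, including Visit 1 (Day 0), Visit 2 (Day 28) and Visit 3 (Day 56) will be analyzed". The ANOVA tables in SAP 7.1 are by visit, so the randomised groups are also tested against each other at Day 0.

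The plan has no covariate, change-from-baseline or repeated-measures model. The sensitivity analysis in SAP 2.6 changes only how values outside the quantification limits are handled. Day 0 enters one derived endpoint, Zika ELISA seroconversion (a 4-fold rise, SAP 5.2). SAP 5.1 lists measles seroconversion, but SAP 5.2 does not define it. SAP 2.5 names GMFI, but SAP 7.1 lists no GMFI table.

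**The concern.** Where participants start from very different titres, part of the spread at Days 28 and 56 was already there at Day 0. A group-only model counts that part as noise. The protocol expects such a mixed start for measles: "large parts of the population have been vaccinated at least once, while some have undergone natural infections" (section 4.6, Potential Benefit). It also calls pre-existing immunity a major point of interest for this vector and names a measles boost as a possible benefit.

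The groups have 14, 14, 12 and 8 participants, so chance differences at Day 0 can be sizeable, above all against the placebo group of 8. At stake is the width of the intervals for the GMT ratios, and how far this one trial's ratios reflect where the groups happened to start.

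**Working it through.** **Inputs from the documents.** Group sizes A 14, B 14, C 12, D 8 (protocol 8.2), total 48. Four groups leave 44 error degrees of freedom, or 43 with one covariate. VNT LLOQ is 20 (protocol Revision Index), and values below it are set to half the limit (SAP 5.2). The plan states no power, effect size, SD or precision target, so there is no planned figure to reproduce.

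**Assumptions.** SD of log10 titre 0.4, with 0.3 to 0.6 as the range, equal at Day 0 and later. The within-group correlation r between Day 0 and later log10 titre runs from 0 to 0.8. The slope is the same in all groups.

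**1. Chance difference at Day 0, A versus D.** Standard error = SD × √(1/14 + 1/8) = 0.443 × SD. At SD 0.4 this is 0.177 log10, and 10^0.177 = 1.50-fold. At SD 0.3 it is 1.36-fold, and at SD 0.6 it is 1.84-fold.

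**2. How much of it reaches the later comparison.** With equal SDs the baseline slope equals r, so the expected carry-over is r × 0.177. At r = 0.5 this is 0.089 log10, a ratio of 1.23. At r = 0.8 it is 0.142 log10, a ratio of 1.39. Across SD 0.3 to 0.6 the carried ratio is 1.17 to 1.36 at r = 0.5 and 1.28 to 1.63 at r = 0.8.

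**3. Precision.** Variance with the covariate relative to the planned ANOVA = (1 − r²) × (1 + 1/42). The second factor is the average price of estimating the slope. Equivalent trial size = 48 ÷ this ratio.

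**4. Limits for A versus D.** Tukey-Kramer critical value = q(0.95; 4 groups)/√2, which is 2.670 at 44 df and 2.672 at 43 df. The planned ANOVA at SD 0.4 gives 2.670 × 0.177 = 0.473 log10, so the GMT ratio is multiplied and divided by 2.97. The SAP ties Tukey-Kramer to the p-values, and these limits match those tests.

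| r | Variance ratio | Equivalent N | Limits, SD 0.4 (planned: 2.97) | Ratio carried from a 1-SE Day 0 difference, SD 0.4 |
|---|---|---|---|---|
| 0 | 1.02 | 47 | 3.02 | 1.00 |
| 0.3 | 0.93 | 52 | 2.87 | 1.13 |
| 0.5 | 0.77 | 63 | 2.60 | 1.23 |
| 0.7 | 0.52 | 92 | 2.20 | 1.33 |
| 0.8 | 0.37 | 130 | 1.94 | 1.39 |

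A simulation of the four-group design gives variance ratios of 0.79, 0.52 and 0.37 at r = 0.5, 0.7 and 0.8, in line with the formula.

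**5. Break-even.** Allowing for the slightly larger critical value, adjustment gains nothing when (1 − r²) × 1.0238 × (2.672/2.670)² = 1, that is at r of about 0.16.

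**6. By assay.** For measles ELISA the protocol itself expects mixed prior immunity, so a real baseline spread is likely. For Zika ELISA the 4-fold-rise definition presumes a usable Day 0 value, but the quantification limits are redacted and the spread is unknown. For Zika VNT, exclusion criteria 3 and 7 remove known Zika or Dengue infection and prior Zika vaccination. Most Day 0 values are therefore likely below 20 and set to the constant 10, which leaves little to carry over or to gain. This is an inference, because no serological screen is listed.

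**The case against.** The strongest reply is that the planned analysis is not wrong. Under randomisation the group-only ANOVA is unbiased on average, and its intervals and p-values already allow for chance imbalance. That stands: the loss is precision, not validity. A reader might infer that the planned comparison is biased, and the documents do not support that.

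A reader might also infer that a Day 0 imbalance passes one-for-one into the later GMT ratio, so that a 1.50-fold false ratio is to be expected. That would need a slope of 1. The 1.50 is the Day 0 difference itself, and what carries over is smaller (step 2).

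Third, the model is written out first for Zika VNT, where adjustment probably does nothing, and measles antibody appears in no stated objective or endpoint. Both are true, and they limit the weight of the point. Every size above also rests on an assumed r and SD. The documents do not show that most of the later measles spread is baseline spread.

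Fourth, the protocol reports that baseline measles titre had no effect on Zika neutralising GMT in the earlier Zika trial (4.4.1) or on the response to the chikungunya vaccine (4.6). Those findings relate measles immunity to a different antibody. They do not say how well a Day 0 titre predicts the later titre in the same assay.

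Finally, Day 0 GMTs are tabulated, so an imbalance would be visible. Seeing it does not correct the ratio, and no other planned GMT comparison does.

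**Conclusion.** The concern holds as a matter of efficiency. The plan leaves out a covariate that it already intends to measure in everyone, apart from missing samples. If r is 0.5 to 0.8, the variance of the ELISA GMT comparisons would fall to 0.77 to 0.37 of that planned, equivalent to a trial of about 63 to 130 instead of 48. A one-standard-error Day 0 difference between A and D would otherwise move the unadjusted ratio by 1.23- to 1.39-fold at SD 0.4. For scale, the protocol reports a final 1.3-fold measles rise over baseline in the three-high-dose group of the earlier trial. That is a within-group change, so it is a benchmark only.

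The gain is clearest for measles ELISA, plausible for Zika ELISA and probably negligible for Zika VNT. Below r of about 0.16 there is none, and at r = 0 the cost is about 2% in variance. The endpoints concerned are secondary or supportive, and the primary safety endpoint is untouched. The between-group test at Day 0 adds nothing, because differences between randomised groups at that point arise by chance.

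**What to change.** In SAP 2.6 and 5.1 and protocol 12.2:

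- For measles ELISA and Zika ELISA at Visits 2 and 3, fit log10 titre = treatment group + log10 Day 0 titre of the same assay. Report adjusted GMTs and GMT ratios with 95% CIs and the same Tukey-Kramer adjustment.
- Use the substitution rule already in SAP 5.2 for Day 0 values outside the quantification limits.
- Keep the unadjusted ANOVA as supportive for the two ELISAs, and as the analysis for VNT.
- Show Day 0 GMTs by group descriptively, without a between-group test.
- State that participants with no Day 0 sample drop out of the adjusted model only.

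No new data are needed. The statistical cost is one degree of freedom. The text change is small, but editing protocol 12.2 means a written amendment under protocol 16.1, and SAP 2.14 must stay consistent with it. If an amendment is not wanted, protocol 12.6 lets the SAP add analyses, so the adjusted model could be added beside the planned one. Either way it should be fixed before titres are seen by treatment group, because SAP 2.4 unblinds the sponsor and analysis team at the preliminary analysis.
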